Protocol Identifying Number:	TP-0020402
Protocol Name:	Tandem Freedom Feasibility Trial #2
Protocol Version / Date:	1.0 / 20 NOV 2024

The Principal Investigators (undersigned) hereby declare that they have read this protocol and agree to its contents.

The investigator agrees that the study will be conducted according to the applicable New Zealand regulations (Medsafe and Health and Disability Ethics Committee), International Conference on Harmonization (ICH) guidelines on Good Clinical Practice (GCP) and the principles of the World Medical Association Declaration of Helsinki 2008. The investigator will conduct all aspects of this study in accordance with all national, state, and local laws or regulations.

By written consent to this protocol, the investigators agree to the above and to fully co-operate with all monitoring and audits in relation to this trial by allowing direct access to all documentation, including source data, by authorized individuals representing Tandem Diabetes Care, Inc., HDEC, Medsafe New Zealand, and/or by the US Federal, State and local regulatory authorities.

Investigator Name: _____

Investigator Signature: _____

Date (DD/MMM/YYYY): _____

PROTOCOL SUMMARY

[figure not shown]
Study Sponsor	Tandem Diabetes Care, Inc.
Protocol Number	TP-0020402
Protocol Title	Tandem Freedom Feasibility Trial #2
Précis	This feasibility study is a prospective, single arm study evaluating the Tandem Freedom system compared to a Control-IQ technology run-in phase in adults with type 1 diabetes. Existing Control-IQ technology users will use Control-IQ technology at home for 1 week, then will use Tandem Freedom in a supervised hotel setting with Dexcom follow active. The goal of Tandem Freedom is to use the system without requiring meal boluses.
Products	Investigational Device: t:slim X2 insulin pump with Tandem Freedom Algorithm
Objectives	The objective of the study is to assess the feasibility of the Tandem Freedom system, by assessing safety and performance in a short-term supervised setting in adults with type 1 diabetes under direct clinical supervision.
Number of Sites	1 Clinical Site in New Zealand
Study Design	Single arm, prospective feasibility study to assess safety.
Number of Participants	Up to 20 participants signing consent to use the study devices, with a goal that at least 10 complete the study.

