Protocol Overview/Synopsis	
After consent is signed, eligibility will be assessed.
 
Run-In Period:
 
After eligibility is assessed, participants will be given a study Dexcom G6 sensor, and will continue to use their Control-IQ system for 7 +/- 3 days at home.
 
Participants will be instructed to bolus for meals as they normally do.
 
Participants will be required to change their CGM sensor 48 +/- 12 hours before the hotel study.
 
Hotel Observed Session
 
Participants will then be admitted for the hotel observed setting for 4 nights.
 
On Day 1, participants will arrive before lunch, where they will bolus for the lunchtime meal as per their usual carb ratio and bolus routine with their home pump.
 
Participants will be switched the Tandem Freedom system, waiting for at least 2 hours after lunch before starting the Freedom system, which uses a t:slim X2 insulin pump and a nearly identical interface participants are familiar with from their home pump, but is now running a new algorithm that is designed to be used without a requirement for meal boluses.
 
Study staff will enable Dexcom follow from participants phones to study medical providers, who will also be physically present.
 
Study staff will program the Tandem Freedom pump TDI average from the last 7-days as shown in their home Control-IQ pump, a sleep schedule, and then enable Tandem Freedom for closed-loop. All participants will be encouraged to use TruSteel infusion sets to minimize chance of occlusion during the study.
 
Participants will bolus for all meals for the remainder of Day 1, entering carbohydrates as they would usually estimate and adjusting their overall bolus amount if needed. All boluses will be reviewed with study staff.
 
On Day 2 - 4, participants will eat meals and snacks as they usually would, but will be encouraged to not bolus for any meals. If a user or study staff feel a meal or correction bolus is needed, the investigator will make this determination and allow for boluses as they determine are needed.

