7 approaches to type 1 diabetes management.

8 1.1.2 Tandem X2 Insulin Pump and Tandem Freedom Control Algorithm

9 The Tandem X2 insulin pump with Control-IQ technology is an approved closed-loop control (CLC)
10 system. Use of the Control-IQ system has been extensively tested in adults and children with type 1
11 diabetes, demonstrating its efficacy and safety when used with insulin lispro (Humalog) or insulin aspart
12 (Novorapid).^{1,2} A recent evaluation of real-world use of the system in 9,451 users age \geq 6 years with at
13 least 12 months of system use found results comparable to those found in the randomized trials.³

14 A next generation CLC algorithm, the Tandem Freedom System, is now being evaluated to remove the
15 burden of meal bolusing. The system is designed to not require meal insulin boluses as part of its design.
16 This algorithm is now running in the t:slim X2 insulin pump.

17 A prior study with the Tandem Freedom system was completed in the supervised setting in New Zealand
18 in June 2024 (NCT06428591). Ten adults with type 1 diabetes (average age 30 years old [range 18 – 64
19 years old], duration of diabetes 18 +/- 13 years, total daily insulin 62 +/- 23 units/day [range 28 – 106
20 units/day], current Control-IQ users for 1.4 +/- 0.5 years, HbA1c 6.8 +/- 0.7% [range 6.0 – 7.9] completed
21 the study. After a Control-IQ run-in period at home, participants were admitted to the hotel for the
22 supervised study, where they used the Tandem Freedom system first with boluses for one day, then
23 without boluses for one, eating large meals and performing exercise each day.

24 The study showed participants achieved 61.8% time in range 3.9-10.0 mmol/L at home using Control-IQ
25 technology during the run-in week, 82.4% time in range 3.9-10.0 mmol/L using Freedom for 24 hours
26 with boluses, and 54.7% time in range 3.9-10.0 mmol/L using Freedom for 24 hours without meal
27 boluses. There were no severe hypoglycemia or DKA events, and no serious adverse events. As
28 participants were able to achieve nearly the same time in range without bolusing with Freedom as they
29 achieved with bolusing with Control-IQ, the results from this study support continued development and
30 evaluation in a second study.

31 1.2 Rationale

32 The objective of this study is to assess the feasibility of the Tandem Freedom system, by assessing safety

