267 On Day 1, participants will arrive before lunch, where they will bolus for the lunchtime meal as per their
268 usual carb ratio and bolus routine with their home pump.

269 Participants will be switched the Tandem Freedom system and be encouraged to use the TruSteel infusion
270 set, waiting for at least 2 hours after lunch before starting the Freedom pump (Investigational Device).

271 Study staff will use the TDI from the last 7 days as shown on the participants home pump to initialize the
272 system, although they may adjust this value per clinical judgement, and re-initialize the system based on
273 an updated TDI at any time during the study.

274 A sleep schedule will be set from 11 PM to 6 AM so sleep activity automatically activates in the evening
275 and deactivates in the morning.

276 Participants will bolus for all meals for the remainder of Day 1, entering carbohydrates as they would
277 usually estimate and adjusting their overall bolus amount if needed.

278 Participants may perform low-intensity activity (e.g., walking) at any time during day 1.

279 No meals should occur after sleep activity is enabled.

280 **3.2.3 Days 2 through 4 – Full Days**

281 Sleep activity will be disabled upon waking up if not already automatically de-activated per the sleep
282 schedule.

283 On Days 2 - 4, participants will eat meals and snacks as they usually would, but will be encouraged to
284 NOT BOLUS for all meals and snacks. If a user or study staff feel a meal or correction bolus is needed,
285 the investigator will make this determination and allow for boluses as they determine are needed.

286 Participants will also be encouraged to perform a supervised brisk walk or similar exercise of at least 45
287 minutes each full day (Day 2 to Day 4) under staff supervision, at approximately the same time each day.
288 Additional exercise per the participants usual routine will be allowed as long as study staff are notified.
289 Exercise activity should be used for this exercise, to start 30-90 minutes before exercise, and turned off
290 after exercise is complete, as determined by the investigator.

291 Exercise does not have to be performed, but will be encouraged. Exercise will be cancelled or stopped at
292 any point for injury or development of new symptoms (development of chest pain/pressure, feeling
293 unwell, development of hypoglycemic symptoms, undue shortness of breath, signs of poor perfusion (leg

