8.4 Outcome Measures

651

The two study periods are:

652

1) Control-IQ at home run-in period.

653

2) The Tandem Freedom hotel observed period.

654

Primary Endpoints for each period:

655

1. Severe hypoglycemia (with cognitive impairment such that assistance of another individual is needed for treatment)

657

2. Number of diabetic ketoacidosis events

658

Secondary Endpoints for each period:

659

1. All device-related adverse events

660

2. CGM hypoglycemia outcomes

661

a. Overall % time <3.0 mmol/L

662

b. Overall % time <3.9 mmol/L

663

3. Times in ranges-overall (3.9-10 mmol/L, >10 mmol/L, >13.9 mmol/L, 3.9-7.9 mmol/L)

664

4. Mean glucose

665

5. Overall variability (CV and SD)

666

Due to the small sample size and feasibility nature of the study, primarily descriptive statistics will be used.

668

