8.5 Baseline Descriptive Statistics

669

Baseline demographic and clinical characteristics of the cohort of participants will be summarized in a table using summary statistics appropriate to the distribution of each variable.

671 **8.6 Additional Tabulations and Analyses**

672 The following data will be tabulated at baseline, for the run-in period, and for the hotel supervised period

- 673 • Insulin metrics (units/kg): total daily insulin, total daily manual insulin.

674 **8.7 Device Issues**

675 The following tabulations will be performed with respect to device issues:

- 676 • Number of device issues by type, and number of unique participants with each type of device issue

677 **8.8 Multiple Comparison/Multiplicity**

678 There are no adjustments performed for multiple comparisons.

679 **8.9 Handling of Missing Data**

680 All practical monitoring and follow-up steps will be taken to ensure complete and accurate data
681 collection. All analyses will be based on available data only; no imputation for missing data is planned.

682

683

Chapter 9: Data Collection and Monitoring

684

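### The planned outputs do not show how many Day 2–4 meals went unbolused, so the hotel time in range cannot be read as no-bolus performance

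*Combined protocol and SAP*

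**What the plan says.** The Précis in the Protocol Summary gives the purpose of the system: "The goal of Tandem Freedom is to use the system without requiring meal boluses". Section 1.2 says the study is meant to learn more about how the system behaves when meals are not bolused and during exercise. The stated objective covers both safety and performance.

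The hotel stay has two bolus regimes:

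- **Day 1 (section 3.2.2).** After the switch to the new system, "Participants will bolus for all meals for the remainder of Day 1, entering carbohydrates as they would" usually estimate them.
- **Days 2–4 (synopsis and section 3.2.3).** In the synopsis, "participants will eat meals and snacks as they usually would, but will be encouraged to not bolus for any meals". Section 3.2.3 repeats the encouragement and adds the discretion: if a bolus is felt to be needed, "the investigator will make this determination and allow for boluses as they determine are needed". That section sets no limit on the number of such boluses and does not ask for a recorded reason.

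The analysis treats the stay as one block. Section 8.4 names the second study period as "2) The Tandem Freedom hotel observed period" and defines the CGM outcomes as overall values per period. Neither section 8.4 nor the synopsis endpoints count bolused or unbolused meals, or split CGM results by day. Section 8.6 adds one relevant tabulation, for baseline, run-in and hotel period: "Insulin metrics (units/kg): total daily insulin, total daily manual insulin".

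**The concern.** A result described as use without meal boluses needs a statement of how many meals were in fact unbolused. Here not bolusing is a request with an open exception, so the number of exceptions is itself a main feasibility finding. The plan does not report it.

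The manual-insulin tabulation does not fill the gap. It is in units/kg, not meals. It does not separate meal boluses from corrections. It does not say whether corrections given by injection, which Table 1 allows, are counted. It also covers a period that contains the planned Day 1 boluses. The same mean could arise from one participant bolusing every meal or from everyone bolusing now and then, and those two patterns say different things about feasibility.

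What is at stake is the reading of the hotel time in range. Section 1.1.2 already sets unbolused time in range beside Control-IQ time in range to support continued development. The same comparison is likely to be made from this study, with a hotel figure whose composition is unknown. The CGM hypoglycemia outcomes are mixed in the same way.

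**Working it through.** The plan has no calculated figure to reproduce: section 8.3 gives at least 10 completers as a convenience sample, and section 8.2 states no hypotheses. The check has two parts.

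**1. What the outputs can show**

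- Meals unbolused on Days 2–4, per participant or overall: not in 8.4, 8.6 or 8.7.
- Participants with no manual bolus on Days 2–4: not planned.
- Time in range for Days 2–4 apart from Day 1: not planned.
- Amount of manual insulin: planned (8.6), but for the whole hotel period.
- Source data for a meal-level count: largely collected. The food diary records the start time of meals (3.2.1), and electronic device files are primary source (9.1).

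**2. How much the mix could matter (illustration)**

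Inputs from the first feasibility study (section 1.1.2), time in range 3.9–10.0 mmol/L: 61.8% on Control-IQ in the run-in week, then on the new system 82.4% over 24 hours "with boluses, and 54.7% time in range 3.9-10.0 mmol/L using Freedom for 24 hours without meal" boluses. Section 3.2.1 provides 3 meals a day, so Days 2–4 contain 3 × 3 = 9 provided meals per participant, or 90 for 10 completers, without snacks.

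Assume these figures carry over and that time in range (TIR) rises in proportion to the share f of meals bolused:

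TIR(f) = 54.7 + (82.4 − 54.7) × f = 54.7 + 27.7 f

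- f = 10%: 57.5%
- f = 20%: 60.2%
- 1 of 9 meals: 57.8%
- 2 of 9 meals: 60.9%
- 3 of 9 meals: 63.9%

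Gap to Control-IQ: 61.8 − 54.7 = 7.1 points. Share of meals that equals it: 7.1 / 27.7 = 25.6%, which is 0.256 × 9 = 2.3 meals per participant, or about 23 of 90.

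Those figures describe Days 2–4 alone, whereas the planned output pools Day 1. Assume that the new system starts at hour s between 14:00 and 16:00 on Day 1, that waking is at hour w between 06:00 and 08:00 on Days 2 and 5, and that the period runs from system start to waking on Day 5:

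- Day 1 segment = (24 − s) + w = 14 to 18 h
- whole period = (24 − s) + 72 + w = 86 to 90 h
- Day 1 share = 14/86 to 18/90 = 16% to 20%
- pooled TIR with no bolus at all on Days 2–4 = 54.7 + 27.7 × share = 59.2% to 60.2%
- meals of 9 that bring the pooled value to 61.8% = 9 × (0.2563 × whole period − Day 1 segment) / 72 = 0.6 to 1.0

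So under these assumptions the pooled figure needs even fewer discretionary boluses to equal the Control-IQ value.

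**The case against.** The best case for the plan is that the information is not lost. Section 8.6 gives a direct, if coarse, measure of manual insulin, and meal times and device files are kept, so a meal-level count could be derived later. Safety is the primary objective, there are no hypotheses, and no success criterion or test against Control-IQ exists for a mixed time in range to corrupt. All of this stands. It limits the weight of the point and rules out a stronger inference that a reader might draw, namely that the no-bolus goal cannot be judged from this study at all. What remains is that no such count is planned, and that in a descriptive study the tabulations are the whole result.

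A reader might also infer that discretionary boluses will go to the worst meals and lift time in range by a known amount. The documents do not support that. Section 3.2.1 has meal boluses given at the participant's usual timing, at most 15 minutes before the meal, so many would be decided before that meal's rise is visible. The hyperglycemia rows of Table 1 act only after glucose has been above 16.7 mmol/L for more than 2 hours, when time out of range has already built up. The linear mix treats such a late correction like a planned meal bolus and so probably overstates its effect. Its inputs are also two single 24-hour periods and one run-in week in ten people who ate large meals, whereas here participants eat as usual; no variance is given.

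Finally, one might want to score a fixed window after each discretionary bolus as out of range. The length of the window would be arbitrary. At 2.3 boluses and 3 to 4 hours each, it would cover 6.9 to 9.2 of 72 hours, or about 10% to 13%, and could charge an infusion-set failure to the algorithm. It is not recommended.

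**Conclusion.** The point holds as a gap in reporting. As planned, the outputs will not show how many Day 2–4 meals were unbolused or by whom, and the hotel time in range mixes planned Day 1 boluses, any discretionary boluses and unbolused meals. It should not be presented as no-bolus performance.

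The size is illustrative: about 26% of meals bolused, or 2.3 of 9, would equal the 7.1-point gap to Control-IQ on Days 2–4. This rests on the first study's figures carrying over and on linear mixing. It is neither a prediction nor an estimate of bias, and its direction and size here depend on which boluses are given and when. The weight is low to moderate, because safety is primary and the analysis is descriptive.

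**What to change.** Add to section 8.4 or 8.6, for Days 2–4 separately from Day 1:

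- (a) number and percentage of recorded meals and snacks with no manual bolus, per participant and overall;
- (b) number and percentage of participants with no manual bolus on all three days;
- (c) a listing of each discretionary bolus, with meal and correction boluses identified separately and injected corrections included, giving time, units, reason and glucose;
- (d) observed time in range for Days 2–4, shown beside (a) and (b).

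The rule linking a bolus to a meal should be written down before the data are seen. No change to when boluses are allowed is proposed.

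The cost is a little more tabulation, an eCRF field for the reason and for any injected dose (which the pump would not log), and an instruction that snacks go into the food diary, since section 3.2.1 names only meals. The reason should be captured at the time, because it cannot be reliably reconstructed afterwards.

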4.1 Study Devices

315

4.1.1 Insulin Pump

316

For the hotel supervised session, participants will use the study provided Tandem t:slim X2 insulin pump with the Tandem Freedom System/algorithm (Investigational Device).

318

4.1.2 Continuous Glucose Monitoring

319

The study CGM is the commercial version of the Dexcom G6 (Dexcom, Inc), which includes a transmitter and sensors. The CGM sensor will be replaced at least once every 10 days.

321

4.1.3 Blood Glucose and Ketone Meter

322

For blood glucose and ketone testing, participants will use their home meter, the CareSens Dual Blood Glucose and Ketone Testing Monitor (i-SENS, Inc).

324

Blood glucose levels will be measured using the blood glucose meter (glucometer) and the CGM device will be calibrated if needed using the glucometer and strips in accordance with the manufacturer's labeling.

327

Blood ketone levels will be measured when needed to evaluate prolonged hyperglycemia.

328

4.1.4 Study Device and Drug Accountability Procedures

329

Device accountability and inventory will be documented to include detailed inventory records of the study CGM supplies, and Tandem insulin pump system.

331

4.1.5 Participant Access to Study Device at Study Closure

332

Participant will return the investigational study device (insulin pump) at study closure. Participant may keep any extra ketone and glucose testing strips they were issued, and any issued remaining pump and CGM supplies that are not marked for investigational use.

335

Chapter 5: Testing Procedures

336

5.1 Laboratory Testing

337

5.1.1 HbA1c

338

HbA1c measurement will be performed locally in clinic or at a laboratory at the screening visit if no prior HbA1c measurement is available from the last 3 months.

340

5.1.2 Urine Pregnancy

341

Urine pregnancy testing performed locally at clinical site for females of child-bearing potential at the screening visit, and anytime pregnancy is suspected.

343

344 Chapter 6: Unanticipated Problem, Adverse Event, and

345

346 Device Issue Reporting

347

348 6.1 Unanticipated Problems

349 Site investigators will promptly report to the Sponsor on an eCRF all unanticipated problems meeting the
350 criteria below. For this protocol, an unanticipated problem is an incident, experience, or outcome that
351 meets all of the following criteria:

- 352
- 353 • Unexpected (in terms of nature, severity, or frequency) given (a) the research procedures that are
354 described in the protocol related documents, such as the HDEC (Health and Disability Ethics
355 Committees)-approved research protocol and informed consent document; and (b) the characteristics
356 of the subject population being studied
 - 357 • Related or possibly related to participation in the research (possibly related means there is a
358 reasonable possibility that the incident, experience, or outcome may have been caused by the
359 procedures involved in the research)
 - 360 • Suggests that the research places participants or others at a greater risk of harm than was previously
361 known or recognized (including physical, psychological, economic, or social harm)

362 The Sponsor will report to the appropriate regulatory authorities if the event meets the criteria of an
363 Unanticipated Problem requiring additional reporting.

364

365 6.2 Adverse Events

366

367 6.2.1 Definitions

368 369 Adverse Event (AE): Any untoward medical occurrence (including laboratory findings) associated with
370 study procedures, the use of a device, biologic in a study participant, including any comparator used,
371 irrespective of the relationship between the adverse event and the device(s) under investigation (referred
372 to as *Adverse Reaction* when caused by a drug).

373 374 Serious Adverse Event (SAE): Any untoward medical occurrence that meets at least one of the following:

- 375
- 376 • Results in death.
 - 377 • Is life-threatening; (a non-life-threatening event which, had it been more severe, might have become
378 life-threatening, is not necessarily considered a serious adverse event).
 - 379 • Requires inpatient hospitalization or prolongation of existing hospitalization.
 - 380 • Results in persistent or significant disability/incapacity or substantial disruption of the ability
381 to conduct normal life functions (sight threatening).
 - 382 • Is a congenital anomaly or birth defect.
 - 383 • Is considered a significant medical event by the investigator based on medical judgment (e.g., may
384 jeopardize the participant or may require medical/surgical intervention to prevent one of the outcomes
385 listed above).

386 387 Unanticipated Adverse Device Effect (UADE): Any serious adverse effect on health or safety or any
388 life -threatening problem or death caused by, or associated with, a device, if that effect, problem, or death
389 was not previously identified in nature, severity, or degree of incidence in the investigational plan or
390 application (including a supplementary plan or application), or any other unanticipated serious problem
391 associated with a device that relates to the rights, safety, or welfare of participants (21 CFR 812.3(s)).

382 Adverse Device Effect (ADE): Any untoward medical occurrence in a study participant which the device
383 may have caused or to which the device may have contributed (Note that an Adverse Event Form is to be
384 completed in addition to a Device Issues Form, unless excluded from reporting as defined in section
385 6.2.2).

386 Comparator: Medical device, therapy (e.g. active treatment, normal clinical practice), placebo or no
387 treatment, used in the control group in a clinical investigation. (ISO 14155:2020)

388 Device Complaints and Malfunctions: A device malfunction or complaint is something that happens
389 to a device or related to device performance, whereas an adverse event happens to a participant. A device
390 complaint may occur independently from an AE, or along with an AE. An AE may occur without a
391 device complaint or there may be an AE related to a device complaint. A device malfunction is any
392 failure of a device to meet its performance specifications or otherwise perform as intended.
393 Performance specifications include all claims made in the labeling for the device. The intended
394 performance of a device refers to the intended use for which the device is labeled or marketed.
395 (21 CFR 803.3). Note: for reporting purposes, sites will not be asked to distinguish between device
396 complaints and malfunctions.

397 Use Error: User action or lack of user action while using the medical device that leads to a different result
398 than that intended by the manufacturer or expected by the user. Includes the inability of the user to
399 complete a task. Use errors can result from a mismatch between the characteristics of the user, user
400 interface, task or use environment. Users might be aware or unaware that a use error has occurred. An
401 unexpected physiological response of the patient is not by itself considered a use error. A malfunction of
402 a medical device that causes an unexpected result is not considered a use error. (ISO 14155:2020)

403 **6.2.2 Reportable Adverse Events**

404 A reportable adverse event includes all events meeting the definition of an adverse event, except for the
405 following:

- 406 • Hypoglycemia and hyperglycemia not meeting the criteria below will not be recorded as adverse
407 events unless associated with an Adverse Device Effect or discontinuation of the study device.
- 408 • Skin reactions from sensor or pump infusion set placement are only reportable if severe and/or
409 required treatment.

410 All reportable AEs—whether volunteered by the participant, discovered by study personnel during
411 questioning, or detected through physical examination, laboratory test, or other means—will be reported
412 on an AE form online. Each AE form is reviewed by the Medical Monitor to assess safety and to verify
413 the coding and the reporting that is required.

414 **6.2.3 Hypoglycemic Events**

415 Hypoglycemia is only reportable as an adverse event when one of the following criteria is met:

- 416 • a hypoglycemic event occurred meeting the following definition of severe hypoglycemia: the event
417 required assistance of another person due to altered consciousness, and required another person to
418 actively administer carbohydrate, glucagon, or other resuscitative actions. This means that the
419 participant was impaired cognitively to the point that he/she was unable to treat himself/herself, was
420 unable to verbalize his/ her needs, was incoherent, disoriented, and/or combative, or experienced
421 seizure or loss of consciousness. These episodes may be associated with sufficient neuroglycopenia to
422 induce seizure or loss of consciousness. If glucose measurements are not available during such an
423 event, neurological recovery attributable to the restoration of glucose to normal is considered
424 sufficient evidence that the event was induced by a low glucose concentration.
- 425 • evaluation or treatment was obtained at a health care provider facility for an acute event involving
426 hypoglycemia, or the participant contacted the site and received guidance following the occurrence of
427 an acute event involving hypoglycemia

428 When a severe hypoglycemia event occurs (as defined above), an Adverse Event Form should be
429 completed. Severe hypoglycemia events should be considered to be serious adverse events with respect to
430 reporting requirements. When a severe hypoglycemia event occurs during use of a study device, it
431 generally will be considered to be unrelated to the device (per section 6.2.5) if the device functioned as
432 intended and there does not appear to be a flaw in how the device is intended to function.

433 **6.2.4 Hyperglycemic/Ketotic Events**

434 Hyperglycemia is only reportable as an adverse event when one of the following criteria is met:

- 435 • the event involved DKA, as defined by the Diabetes Control and Complications Trial (DCCT) and
436 described below
- 437 • evaluation or treatment was obtained at a health care provider facility for an acute event involving
438 hyperglycemia or ketosis, or the participant contacted the site and received guidance on how to
439 manage the hyperglycemia/ketosis
- 440 • blood ketone level ≥ 1.0 mmol/L, even if there was no communication with a health care provider at
441 the time of the event

442 Hyperglycemic events are classified as DKA if all of the following are present, or judged likely to have
443 been present based on available data:

- 444 • Symptoms such as polyuria, polydipsia, nausea, or vomiting;
- 445 • Serum ketones > 1.5 mmol/L or large/moderate urine ketones;
- 446 • Either arterial blood pH < 7.30 or venous pH < 7.24 or serum bicarbonate (or CO₂) < 15 ; and
- 447 • Treatment provided in a health care facility

448 When a hyperglycemia/ketotic event qualifies as an AE, or as a SAE as defined in section 6.2.1, an
449 Adverse Event Form should be completed. Events meeting DKA criteria should be considered to be
450 serious adverse events with respect to reporting requirements. Hyperglycemia events not meeting criteria

451 for DKA generally will not be considered as serious adverse events unless one of the SAE criteria in
452 section 6.2.1 is met.

453 When a hyperglycemia/DKA event occurs during use of a study device, it generally will be considered to
454 be unrelated to the device (per section 6.2.5) if the device functioned as intended and there does not
455 appear to be a flaw in how the device is intended to function.

456 **6.2.5 Relationship of Adverse Event to Study Investigational Device**

457 The study investigator will assess the relationship of any adverse event to the study device or study drug.
458 The Medical Monitor also will make this assessment, which may or may not agree with that of the study
459 investigator. Reporting requirements will be based on the Medical Monitor's assessment.

460 To ensure consistency of adverse event causality assessments, investigators should apply the following
461 general guidelines when determining whether an adverse event is related to a study device or study drug:

462 **Unrelated:** The AE is clearly not related to a study drug/device and a likely alternative etiology exists
463 such as an underlying disease, environmental or toxic factors or other therapy.

464 **Unlikely Related:** The AE does not follow a reasonable temporal sequence during or after use of study
465 drug/device and a more likely alternative etiology exists such as an underlying disease, environmental or
466 toxic factors, or other therapy.

467 **Possibly Related:** The AE occurred in a reasonable time during or after use of study drug/device; but
468 could be related to another factor such as an underlying disease, environmental or toxic factors, or other
469 therapy; and there is a possible, though weak, scientific basis for establishing a causal association
470 between the AE and the study drug/device.

471 **Probably Related:** The AE occurred in a reasonable time during or after use of study drug/device; is
472 unlikely to be related to another factor such as an underlying disease, environmental or toxic factors, or
473 other therapy; and there is a plausible, though not strong, scientific basis for establishing a causal
474 association between the AE and the study drug/device.

475 **Definitely Related:** The AE occurred in a reasonable time during or after use of study drug/device;
476 cannot be explained by another factor such as an underlying disease, environmental or toxic factors, or
477 therapy; and there is a strong scientific basis for establishing a causal association between the AE and the
478 study drug/device.

479 Events determined to be *Possibly Related*, *Probably Related*, or *Definitely Related* will be considered
480 'Related' with respect to any required HDEC and Medsafe reporting.

481 **6.2.6 Severity (Intensity) of Adverse Events**

482 The severity (intensity) of an adverse event will be rated on a three-point scale: (1) mild, (2) moderate,
483 or (3) severe. A severity assessment is a clinical determination of the intensity of an event. Thus, a severe
484 adverse event is not necessarily serious. For example, itching for several days may be rated as severe, but
485 may not be clinically serious.

486 **MILD:** Usually transient, requires no special treatment, and does not interfere with the participant's daily
487 activities.

488 **MODERATE:** Usually causes a low level of inconvenience, discomfort or concern to the participant
489 and may interfere with daily activities, but is usually ameliorated by simple therapeutic measures and
490 participant is able to continue in study.

491 **SEVERE:** Interrupts a participant's usual daily activities, causes severe discomfort, may cause
492 discontinuation of study device, and generally requires systemic drug therapy or other treatment.

493 **6.2.7 Expectedness**

494 For a serious adverse event that is considered possibly related to study device, the Medical Monitor will
495 classify the event as unexpected if the nature, severity, or frequency of the event is not consistent with the
496 risk information previously described in the protocol, labeling, or Investigator Brochure.

497 **6.2.8 Coding of Adverse Events**

498 Adverse events will be coded using the MedDRA dictionary.

499 **6.2.9 Outcome of Adverse Events**

500 The outcome of each reportable adverse event will be classified by the investigator as follows:

- 501 • RECOVERED/RESOLVED – The participant recovered from the AE/SAE without sequelae. Record
502 the AE/SAE stop date.
- 503 • RECOVERED/RESOLVED WITH SEQUELAE – The event persisted and had stabilized without
504 change in the event anticipated. Record the AE/SAE stop date.
- 505 • FATAL – A fatal outcome is defined as the SAE that resulted in death. Only the event that was the
506 cause of death should be reported as fatal. AEs/SAEs that were ongoing at the time of death;
507 however, were not the cause of death, will be recorded as “resolved” at the time of death.
- 508 • NOT RECOVERED/NOT RESOLVED (ONGOING) – An ongoing AE/SAE is defined as the event
509 was ongoing with an undetermined outcome.

510 *An ongoing outcome will require follow-up by the site in order to determine the final outcome
511 of the AE/SAE. The outcome of an ongoing event at the time of death that was not the cause of
512 death, will be updated and recorded as “resolved” with the date of death recorded as the stop
513 date.*

- 514 • UNKNOWN – An unknown outcome is defined as an inability to access the participant or the
515 participant’s records to determine the outcome (for example, a participant that was lost to follow-up).

516 If any reported adverse events are ongoing when a participant completes the study (or withdraws),
517 adverse events classified as UADEs or related SAEs or SUSARs will be followed until they are either
518 resolved, or have no prospect of improvement or change, even after the participant has completed all
519 applicable study visits/contacts. For all other adverse events, data collection will end at the time the
520 participant completes the study. Note: participants should continue to receive appropriate medical care
521 for an adverse event after their participation in the study ends.

522 **6.3 Reportable Device Issues**

523 All UADEs and ADEs as defined in section 6.2.1 will be reported as both ‘device issues’ and adverse
524 events, except for skin reactions from CGM sensor placement or pump infusion set placement that do not
525 require pharmacologic treatment.

526 Device issues will be reported except in the following circumstances. These occurrences are expected and
527 will not be reported on a Device Issue Form assuming criteria for a UADE or ADE have not been met:

- 528 • CGM sensor lasting fewer days than expected per manufacturer
- 529 • CGM tape adherence issues
- 530 • Pump infusion set insertion lasting fewer days than expected per manufacturer
- 531 • Battery lifespan deficiency due to inadequate charging or extensive wireless communication

- 532 • Intermittent device component disconnections/communication failures not requiring system
533 replacement or workaround/resolution not specified in protocol.
534 • Device issues clearly addressed in the protocol that do not require additional troubleshooting

535 **6.4 Timing of Event Reporting**

536 SAEs possibly related to a study device, study drug, or study participation and UADEs must be reported
537 by the site to the Sponsor within 1 working day of the site becoming aware of the event. This can occur
